However, in view of the use of a formula (liquid) low energy diet in the intensive weight loss group, as well as more attention provided from the dietitians, blinding of staff or participants will not be feasible. As a consequence, the possible influence of performance bias on patient-reported outcomes will be discussed as a possible limitation.

Statistical methods

Data will be analysed according to a pre-established statistical analysis plan (SAP). Primary analyses will be done on a modified ITT population, which include all randomised individuals who had the respective variable assessed at baseline. All analyses will be analysed and reported as two-sided, done at a 5% significance level.

We will use analysis of covariance (ANCOVA) for the continuous outcome measures modelled using repeated-measures (mixed linear model) analysis. The statistical model will include diet group (ID/CD) as fixed effects, an interaction between time and diet group, and the respective variable (e.g. body weight at baseline) as assessed at randomisation as covariate. Furthermore, the possible impact on the effect size of the factors used for the stratified randomisation will be explored, i.e. sex (M/ F), obesity class ($<40/\geq40$ kg/m 2), and SU level ($< 6/\geq6$ mg/dL). We aim to assess whether data provide evidence of superiority of ID to CD group (primary objective). Thus, the primary null hypothesis is no difference between treatments at endpoint (week 16). Response variables (binary outcomes; e.g. the proportion of patients losing more than 5% of baseline weight) will be analysed with a logistic regression model, including the same fixed effects (covariates) as for the analyses of continuous outcomes.

Data monitoring

Careful conduct of the clinical trial according to this protocol has a major impact on the credibility of the results. Careful monitoring will ensure that difficulties are noticed early and their occurrence or recurrence minimised. There are two distinct types of monitoring that generally characterise RCTs: (1) The oversight of the quality of the trial, while the other type involves (2) Breaking the blinding to make treatment comparisons (that is, interim analysis). Both types of trial monitoring, in addition to entailing different staff responsibilities, involve access to different types of trial data and information, and thus different principles apply for the control of potential statistical and operational bias.

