## Objectives

Primary efficacy objective: To compare the effect of intensive weight loss, relative to the control group, on changes in body weight from baseline to week 16, in patients with gout and concomitant obesity.

Key secondary efficacy objectives: To compare the effect of intensive weight loss, relative to the matched control group, on changes in serum urate, changes in VAS-fatigue, and changes in VAS-Pain from baseline to week 16, in patients with gout and concomitant obesity.

Other secondary objectives: To explore the effect of the intensive weight loss, relative to the matched control group, on all the following exploratory secondary outcomes:

- proportion of participants maintaining serum urate levels <6mg/dL at visit week 8 and week 16
- percentage reduction in serum urate (%) at final visit (week 16)
- the proportion of individuals with any gout flare in the FIRST 8 weeks following randomization
- the proportion of individuals with any gout flare in the LAST 8 weeks following randomization
- the number of gout flares during the trial period for each patient (up to week 16)
- change in functional status (HAQ) from baseline to week 16
- change in patient global (VAS) from baseline to week 16
- change in swollen joint count (SJC) from baseline to week 16
- change in tender joint count (TJC) from baseline to week 16
- change in number of tophi from baseline to week 16
- change in 36-Item Short Form Health Survey SF-36: Mental Component Scale (MCS) from baseline to week 16
- change in 36-Item Short Form Health Survey SF-36: Physical Component Scale (PCS) from baseline to week 16.

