## Timing of outcome assessments

The schedule of study procedures included is given in the table below.

| VARIABLE                                   | Screening
(approx. -2
wks) | Baseline
(0 wks) | Intermediate
(8 wks) | Endpoint
(16 wks) |  |
|--|----------------------------------|---------------------|-------------------------|----------------------|--|
| Secretariat:                        |                                  |                     |                         |                      |  |
| Information                                |                                  |                     |                         |                      |  |
| Motivational appraisal                     |                                  |                     |                         |                      |  |
| Eligibility criteria/Screening (phone)     | X                                |                     |                         |                      |  |
| Demographics and clinical features: |                                  |                     |                         |                      |  |
| Age, years                                 |                                  | X                   |                         |                      |  |
| Male, y/n                                  |                                  | X                   |                         |                      |  |
| Ethnicity, n (%)                           |                                  | X                   |                         |                      |  |
| Duration of gout, years                    |                                  | X                   |                         |                      |  |
| Height, cm                                 |                                  | X                   |                         |                      |  |
| Body mass index, kg/m          |                                  | X                   | (X)                     | (X)                  |  |
| Flares* in the preceding year, count       |                                  | X                   |                         |                      |  |
| Presence of palpable tophi, y/n            |                                  | X                   | X                       | X                    |  |

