| Concurrent medication:              |                                  |                     |                         |                      |  |
| Diuretics y/n                              |                                  | X                   |                         |                      |  |
| Aspirin y/n                                |                                  | X                   |                         |                      |  |
| Antihypertensive medication y/n            |                                  | X                   |                         |                      |  |

|   |  |   |   |   |
|---|--|---|---|---|
| Lipid lowering agents y/n                                 |  | X |   |   |
| Diabetes medication y/n                                   |  | X |   |   |
| Blood tests (lab. work):†                          |  |   |   |   |
| Creatinine, mg/dL   |  | X | X | X |
| eGFR, mL/min/1.73m                            |  | X | X | X |
| Serum urate, mg/dL  |  | X | X | X |
| Physical examination (Nurse):                      |  |   |   |   |
| Flares* in the last 8 weeks, count                        |  | X | X | X |
| Body weight, kg   |  | X | X | X |
| Touch screen (PROMs):                              |  |   |   |   |
| SF-36 health survey, score                                |  | X | X | X |
| Activity limitation (HAQ), score                          |  | X | X | X |
| Pain (VAS), mm  |  | X | X | X |
| Patient global (VAS), mm                                  |  | X | X | X |
| Fatigue (VAS), mm   |  | X | X | X |
| Physical examination (MD):                         |  |   |   |   |
| ACR/EULAR gout classification                             |  | X |   |   |
| Gout according to expert opinion                          |  | X |   |   |
| Swollen joint count, 0-66                                 |  | X | X | X |
| Tender joint count, 0-68                                  |  | X | X | X |
| Palpable tophi count                                      |  | X | X | X |
| Randomisation (after confirming written informed consent) |  | X |   |   |
| Harms and adverse events‡ (AEs):                   |  |   |   |   |
| Withdrawal, y/n   |  |   | X | X |
| Withdrawal due to AEs, y/n                                |  |   | X | X |
| Number of serious adverse events, count                   |  |   | X | X |
| Death, y/n  |  |   | X | X |

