#### Baseline patient characteristics

Patients will be described with respect to all variables shown in Table 1 in 'Proposed outline of tables and figures' below, separately for the two randomized groups. Data from the baseline visit will be used.

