### Analysis methods

For the primary and key secondary outcomes, we will use analysis of covariance (ANCOVA) modelled using repeated-measures mixed linear model analysis. Statistical tests inferring from P-values will be performed in sequence until one of the analyses has failed to show the significant difference or all analyses have been completed at a significance level of 0.05. The sequence of the analyses for the selected secondary efficacy endpoints are listed as: (1) Change in body weight; (2) Change in serum urate; (3) Change in VAS Fatigue. (4) Change in VAS Pain. The statistical model will include diet group (ID/CD) and time (in weeks) as fixed effects, and the interaction between time and diet group, with the respective variable (e.g. body weight at baseline) as covariate. Furthermore, the possible impact of the factors used for the stratified randomization will be explored, i.e. sex (M/ F), obesity class (<40/≥40 kg/m^2), and SU level (< 6/≥6 mg/dL) but will not be considered part of the primary model. We aim to assess whether data provide evidence of superiority of ID to CD group (primary objective). Thus, the null hypothesis is no difference

between treatments at endpoint (week 16). Response variables and adverse events (binary outcomes) will be analyzed by comparing the proportions responding in each group with the Risk Difference (and 95% CI's), with no further adjustments for covariates.

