| Other secondary outcomes | On treatment target, n(%)*          |              |              |                       | n.a.    |
|                          | Serum urate reduction, %            |              |              |                       | n.a.    |
|                          | VAS patient global                  |              |              |                       | n.a.    |
|                          | HAQ                                 |              |              |                       | n.a.    |
|                          | Swollen joint count                 |              |              |                       | n.a.    |
|                          | Tender joint count                  |              |              |                       | n.a.    |
|                          | Palpable tophi                      |              |              |                       | n.a.    |
|                          | SF-36 MCS                           |              |              |                       | n.a.    |
|                          | SF-36 PCS                           |              |              |                       | n.a.    |

Abbreviations: ID - Intensive diet, CD – conventional diet.

1: Continuous outcome estimates will be derived from the repeated measures linear mixed models where missing data in the ITT population is handled implicitly; the inference will be provided as the difference between least squares means with 95 CI's around them.

2: Dichotomous outcomes will be reported directly as observed (no imputations); the inference will be provided (unadjusted as the difference between proportions, i.e. Risk Difference, with 95% confidence interval).

\*Defined as having a serum urate < 6.0 mg/dL at both week 8 *AND* week 16

**Table 3:** Adverse events and harms

| Event                              | ID
(n=XX) | CD
(n=XX) | Difference (95%CI) |
|------------------------------------|--------------|--------------|--------------------|
| Self-reported flare, 0-16 weeks    |              |              |                    |
| First 8 weeks (0-8)                |              |              |                    |
| Last 8 weeks (8-16)                |              |              |                    |
| Other                              |              |              |                    |
| Serious Adverse Events, 0-16 weeks |              |              |                    |

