| Death                              |              |              |                    |

Abbreviations: ID - Intensive diet, CD – conventional diet.

These dichotomous adverse outcomes will be reported directly as observed (no imputations) with number and percentages; the inference will be provided (unadjusted) as difference between proportions (i.e. Risk Difference, with 95% confidence interval).

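### Pre-trial flare counts are collected but neither tabulated nor used, so a chance imbalance in flare-prone patients would go unseen and uncorrected

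*SAP*

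**What the plan says.** **Collected.** The SAP schedule (Section 3, Timing of outcome assessments) lists "Flares* in the last 8 weeks, count" at baseline, week 8 and week 16, and "Flares* in the preceding year, count" at baseline. The baseline 8-week window therefore has the same length as the two on-trial windows.

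**Shown.** SAP, Baseline patient characteristics, states: "Patients will be described with respect to all variables shown in Table 1". Table 1 has no flare row. The other listed outcomes have a baseline counterpart there: weight, serum urate (SU), fatigue, gout pain, global VAS, HAQ, both joint counts, tophi and both SF-36 scores. Table 3 shows flares for weeks 0-16, 0-8 and 8-16 only.

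**Analysed.** SAP, Analysis methods, compares binary outcomes and adverse events by risk difference "with no further adjustments for covariates". The note to Table 3 repeats this for flares: "the inference will be provided (unadjusted) as difference between proportions". The protocol (Statistical methods) had instead planned logistic regression "including the same fixed effects (covariates) as for the analyses of continuous outcomes", and its continuous models carry the baseline value of the outcome concerned. The SAP gives no reason for the change.

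**Allocated.** Randomisation is 1:1 against a concurrent control and is stratified by sex, obesity class and SU level, not by flare history (SAP, Trial design and Randomization).

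**The concern.** Gout flares recur in the same patients, so flare history is a natural candidate for predicting on-trial flares. With 60 patients and no stratification on that history, one arm may by chance hold more flare-prone patients. The planned tables would not show it, and the planned estimate would not allow for it. A reader of Table 3 who saw a flare difference, or none, could not judge how far the starting position contributed.

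This matters more for flares than for most secondary outcomes because the SAP counts them twice: as an efficacy outcome (Objectives) and as a harm (Harms and adverse events). The omission also looks unintended, since Table 1 gives a baseline value for the other outcomes and the protocol had foreseen adjustment.

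**Working it through.** **Inputs from the documents.** 60 patients, 30 per arm (SAP, Power and sample size). The stated power of 0.888 for body weight reproduces: noncentrality 5/(6.0 × √(2/30)) = 3.23 on 58 degrees of freedom gives 0.8876 by two-sample t-test. The documents give no flare rate, power or sample-size figure, so there is no flare figure to reproduce.

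**Assumptions for steps 2 to 4.** 40% of patients had a flare in the 8 weeks before randomisation (range 30 to 50%). The on-trial 8-week flare risk is 50% with such a flare and 15% without (range 40/20 to 60/10).

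**Step 1: is the raw comparison biased?** This was simulated with 20,000 trials per scenario, 30 per arm and no diet effect. Patient flare rates were gamma-distributed (shape 0.5, 1 or 2; mean 0.2, 0.5 or 1.0 flares per 8 weeks), with Poisson flares before entry and over weeks 0-16. The mean raw risk difference was -0.002 to +0.001, and the 95% Wald interval excluded zero in 5.1 to 6.2% of trials. So there is no bias; the small excess over 5% belongs to the Wald interval at this sample size.

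**Step 2: how often is there an imbalance?** The SD of the between-arm difference in prior-flare share is √(2p(1-p)/30). The chance of a gap of 15 points or more uses the normal approximation.

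| p | SD | Chance of a gap ≥ 15 points |
|---|---|---|
| 0.30 | 0.118 | 0.20 |
| 0.40 | 0.126 | 0.24 |
| 0.50 | 0.129 | 0.25 |

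**Step 3: what does it do to the result?** Shift = 0.15 × (risk with prior flare - risk without).
- Central: 0.15 × 0.35 = 0.052.
- Range: 0.15 × 0.20 = 0.030 to 0.15 × 0.50 = 0.075.

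**Step 4: what precision is at stake?**
- On-trial risk: P = 0.4 × 0.50 + 0.6 × 0.15 = 0.29.
- Raw 95% half-width: 1.96 × √(2 × 0.29 × 0.71/30) = 0.23.
- Variance explained by prior flare: 0.24 × 0.35² / (0.29 × 0.71) = 0.14 (range 0.04 to 0.29).
- Confidence interval ratio: √(1 - 0.14) = 0.93 (range 0.85 to 0.98), so 23 points becomes about 21.

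This formula ignores the cost of estimating the covariate effect in a small sample.

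**Step 5: cross-check from the simulation.** Correlations between prior and on-trial flare were 0.10 to 0.49.
- A gap of 20 points or more occurred in 5 to 15% of trials.
- A 20-point gap moved the raw difference by 2.4 to 9.7 points. Multiplying by 0.75 gives 1.8 to 7.3 points for a 15-point gap, close to step 3.
- Adjusting for any versus no prior flare (linear adjustment) changed the variance by a factor of 0.78 to 1.01, equivalent to about 60 to 77 patients instead of 60. The gain vanishes where flares are uncommon and the correlation is weak.

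Both calculations assume simple 1:1 allocation. If the stratification factors predict flares, imbalances would be somewhat rarer.

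**The case against.** **The trial already has a control group.** A reader might infer that the flare results cannot separate a diet effect from the patients' earlier flare course. The documents do not support that. Allocation is random and the control arm is concurrent, and step 1 shows the raw difference centred on zero without adjustment. Chance imbalance is also part of what the planned 95% interval covers over repeated trials. This stands in full. What remains is that, in the one trial actually run, an imbalance could be neither seen nor allowed for.

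**Each arm need not be read against its own previous 8 weeks.** That reading is also tempting, but the comparator is the other arm in the same window, and Table 3 already separates weeks 0-8 from 8-16. A pre-trial row beside these would invite a before/after reading. The protocol's lay summary of eligibility asks for a flare in the previous 12 months, so regression to the mean could produce a fall in both arms. Ascertainment differs too: pre-trial flares are recalled, while on-trial flares are also adverse events, and the intensive arm is seen weekly at least in its first phase against three sessions for the control arm. This stands.

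**Related severity is already visible.** Table 1 shows SU, gout duration, tophi, urate-lowering and anti-inflammatory treatment, pain and joint counts, and SU is a stratification factor. This stands in part: these are indirect markers, and none is flare history.

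**One unadjusted rule for all binary outcomes is a legitimate choice at this size.** Flares are outside the test sequence, have no P-value, and the shift is under a quarter of the half-width (5.2/23 = 0.23). This stands as a reason to keep the raw estimate. It is no reason to leave out a baseline value already collected.

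**Conclusion.** The point holds as a modest one about visibility and precision, not about validity. Both pre-trial flare counts are collected, no planned output shows them, no planned analysis uses them, and the SAP drops the protocol's adjustment without explanation.

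On the assumed rates, about one trial in four or five would have an imbalance of 15 points or more in prior flares, moving the risk difference by about 3 to 7.5 points. That is small beside a half-width of about 23 points, but a reader could not see it. Adjustment ranges from no gain (variance factor 1.01) to a useful one (0.78). All these sizes depend on flare rates that the documents do not give.

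The change is worth making. The primary and key secondary conclusions do not depend on it.

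**What to change.** Before the final analysis:

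1. Add two rows to SAP Table 1, by arm: any flare in the 8 weeks before randomisation, and number of flares in the preceding year. The second also shows how far the protocol's 12-month flare condition was met; the SAP's eligibility text omits that condition.
2. In Table 3, beside each planned raw flare risk difference (weeks 0-8, 8-16 and 0-16), give the difference adjusted for any versus no flare in the previous 8 weeks, by Mantel-Haenszel over the two strata, with its 95% confidence interval.
3. State in Analysis methods that the raw difference is kept, and why the protocol's logistic model was replaced.

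Do not add a pre-trial flare row to Table 3. Flares stay outside the four-step test sequence, without P-values.

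The cost is SAP wording, two table rows, one extra column and a simple stratified calculation. The data are already scheduled for collection. The worst simulated loss of precision was about 1% in variance, and the raw estimate remains available. The per-patient flare count, listed as an outcome but with no model or table row, is a separate gap that this change does not close.

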## Prespecified Appendices

**SAP-Appendix Table 1:** Changes in primary and key secondary endpoints (using non-responder imputation)

### Change from baseline

|                               | Outcome            | ID
(n=XX) | CD
(n=XX) | Difference (95%CI) | P-
value |
|-------------------------------|--------------------|--------------|--------------|--------------------|-------------|
| Primary outcome        | Weight loss, kg    |              |              |                    |             |
| Key secondary outcomes | Serum urate, mg/dL |              |              |                    |             |
|                               | VAS fatigue        |              |              |                    |             |
|                               | VAS pain gout      |              |              |                    |             |

Values are least squares means (SE), unless otherwise stated. Abbreviations: ID – intensive diet, CD – conventional diet.

1: Continuous outcome estimates will be derived from the repeated measures linear mixed models where missing data in the ITT population is handled explicitly with a non-responder imputation (i.e. baseline observation carried forward; indicative of a possible NMAR issue); the inference will be provided as the difference between least squares means with 95% CI's around them.

**SAP-Appendix Table 2:** Changes in primary and key secondary endpoints (using 2-sample t-tests)

|                               |                    | Change from baseline  |              |                    |         |
|-------------------------------|--------------------|-----------------------------------|--------------|--------------------|---------|
|                               | Outcome            | ID
(n=XX)                      | CD
(n=XX) | Difference (95%CI) | P-value |
| Primary outcome        | Weight loss, kg    |                                   |              |                    |         |
| Key secondary outcomes | Serum urate, mg/dL |                                   |              |                    |         |
|                               | VAS fatigue        |                                   |              |                    |         |
|                               | VAS pain gout      |                                   |              |                    |         |

Values are means (SD). Abbreviations: ID – intensive diet, CD – conventional diet.

1: Continuous outcomes estimates will be derived from descriptive statistics and 2-sample t-tests (change from baseline at 16 weeks) where missing data is handled explicitly by excluding participants with missing data for any of the four outcomes while still respecting the original treatment allocation (i.e. valid assuming data is missing completely at random); the inference will be provided as the difference group means with 95% CI's around them.

**SAP-Appendix Table 3:** Changes in primary and key secondary endpoints (adjusted for the three stratifying factors)\*

|                               |                    | Change from baseline  |              |                    |         |
|-------------------------------|--------------------|-----------------------------------|--------------|--------------------|---------|
|                               | Outcome            | ID
(n=XX)                      | CD
(n=XX) | Difference (95%CI) | P-value |
| Primary outcome        | Weight loss, kg    |                                   |              |                    |         |
| Key secondary outcomes | Serum urate, mg/dL |                                   |              |                    |         |
|                               | VAS fatigue        |                                   |              |                    |         |
|                               | VAS pain gout      |                                   |              |                    |         |

Values are least squares means (SE), unless otherwise stated. Abbreviations: ID – intensive diet, CD – conventional diet.

\*Based on the same statistical model as the primary analyses (Table 2); adding three further covariates corresponding to the stratified analysis.

1: Continuous outcome estimates will be derived from the repeated measures linear mixed models where missing data in the ITT population is handled explicitly with a non-responder imputation (i.e. baseline observation carried forward); the inference will be provided as the difference between least squares means with 95% CI's around them.
